3.3 Timing of Interim Analysis and Design Adaptations

An interim analysis will be planned when approximately participants in each arm complete the Day 113 (Week 16) assessments. The purpose of the interim analysis would be to obtain early information for planning the phase 3 program. No study conduct will be modified based on interim analysis results.

The interim analysis will evaluate the percentage change in EASI from baseline to Day 113 (Week 16) and proportions of participants with EASI 75 at Day 113 (Week 16), as well as the other available data as needed. Details will be documented in the statistical analysis plan (SAP).

3.4 Definition of End of Study

The EOS is defined as the last patient undergoing the last visit of the study. This will either be:

• Day 169 (Week 24) (or earlier termination) for those patients who do **not** achieve ≥ EASI 75 or IGA 0/1 at Day 169 (Week 24), and are subsequently enrolled in the LTE;

Or

• Day 281 (Week 40) (or earlier termination) for those patients who do **not** achieve ≥ EASI 75 or IGA 0/1 at Day 169 (Week 24), and are **not** enrolled in the LTE and have additional safety follow-up to a total of 140 days after the last dose of IMP;

Or

Day 365 (Week 52) (or earlier termination) for those patients who achieve ≥ EASI 75 or who attain IGA 0/1 at Day 169 (Week 24) and continue on either their pre-Week 24 dose/interval or enter the withdrawal arm, experience loss of clinical response at or after Day 197 (Week 28) and are enrolled in the LTE. Those patients not enrolled in the LTE will have additional safety follow-up to a total of 140 days after the last dose of IMP;

Or

• Day 477 (Week 68) (or earlier termination) for those patients who reach Day 365 (Week 52), are still considered to be responding to study treatment, and are **not** enrolled in the LTE and have additional safety follow-up to a total of 140 days after the last dose of IMP.

3.5 Early Study Termination

The study can be terminated at any time for any reason by the Sponsor (including approval or the favourable opinion is revoked, in the event of a negative change in the benefit/risk ratio when the necessary adjustment to the maximum sum insured is not possible; failure to enrol; futility; safety decision etc). If the trial is suspended or terminated early, the Investigator will promptly inform the trial patients and should assure appropriate therapy and follow-up.

No further IMP will be given to a patient if any study permanent discontinuation rules are met (see Section 9.1), including recommendation of the Independent Data Monitoring Committee (IDMC; Section 3.8). If a patient withdraws from the study treatment early but consent is retained, study assessments may be continued until a) Day 169 (Week 24) for patients who withdraw from study treatment during the first study period and therefore are **not** eligible for

Version number: 1

1-Mar-2022

LTE, or b) until Day 365 (Week 52) or the end of the safety follow-up period in patients who withdraw from study treatment after Day 169 (Week 24).

Unless patients continue in the LTE at Day 169 (Week 24) or due to loss of clinical response at or after Day 197 (Week 28), a safety follow-up for 140 days after the last dose of IMP will be required.

In addition, the Investigator may withhold further IMP from a patient if they report moderate-or-severe (regardless of seriousness) adverse reactions which are attributed to the IMP. There will be no obligation to unblind treatment allocation in making this decision.

The Sponsor may discontinue the entire study at any time based on information received during the running of the study that demonstrates an unexpected risk or absence of benefit to patients. This may for example follow the request of the IDMC or where additional information emerges either during the study or from other sources (eg, literature or Health Authorities).

If the study is discontinued, where patients withdraw early or where IMP has been discontinued by the Investigator, patients will be required to be followed-up for a minimum of 140 days for safety evaluation.

Further details of IMP discontinuation are provided in Section 9.1.

3.6 Randomisation

The Investigator must follow the study randomisation procedures when assigning patients to treatment within the study.

The patient randomisation list will be generated by PPD using Statistical Analysis System (SAS®).

All patients who have completed all Screening assessments and are confirmed as eligible by the Investigator will be randomised to treatment at Baseline. In cases where screen failure occurs due to a laboratory abnormality and is due to reasons expected to change at re-screening and based upon the Investigator's clinical judgment, the patient may be re-screened one time for this study following notification to the Sponsor. Randomisation may be performed up to 24 hours prior to the first administration of KY1005 if all inclusion/exclusion criteria have been satisfied. Each of the 5 treatment regimens (see Table 5-1) will comprise approximately 70 patients (based on 30% drop out rate to Day 169 [Week 24], it is assumed that 49 patients will complete the study) who will be allocated to treatment with KY1005 or Placebo in an equal (1:1:1:1) ratio.

Patients will be centrally randomised. Once confirmed as eligible for the study, patients will be allocated a randomisation number using an IRT system, corresponding to the next available randomised treatment, in a consecutive order starting with the lowest number.

The randomisation will be stratified by disease severity (moderate/severe) and region.

Further randomisation will occur at Day 169 (Week 24) in those patients who achieve ≥ EASI 75 or who attain IGA 0/1. Patients will be randomised in a 3:1 ratio to either enter a withdrawal cohort (receiving Placebo Q4W) or to remain on their pre-Week 24 dose/interval. This Day 169 (Week 24) randomisation will be stratified by IGA response (IGA 0/1 or IGA 2, 3, 4).

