In those patients who achieve ≥ EASI 75 or who attain IGA 0/1 at Day 169 (Week 24), a randomisation will occur pre-dose at Day 169 (Week 24) and patients will enter the second study period. This will occur irrespective of whichever dose group the patient was randomised to at Baseline including Placebo. Patients will be randomised in a 3:1 manner to be withdrawn from therapy or to continue their pre-Week 24 dose/interval. To maintain the blind, those patients randomised to the Withdrawal arm will receive Placebo Q4W. Those patients who are re-randomised at Day 169 (Week 24) who lose their clinical response will be offered the opportunity to be retreated with KY1005 in the LTE study. Loss of clinical response is defined as the first instance of <EASI 50 during the second study period and where rescue therapy is no longer permitted as per Section 5.3.4. If loss of clinical response from Day 197 (Week 28) occurs, Investigators will be able to choose to discontinue the patient from KY1005-CT05

At Day 365 (Week 52), patients who have completed the post-Week 24 period and have not experienced loss of clinical response will have an additional 112 days' safety follow-up up to Day 477 (Week 68) and then be discharged from the study. The last dose will be given no later than Day 337 (Week 48) and as such safety follow-up will be 140 days following last dose of IMP. If during safety follow-up or after the end of study this cohort of patient's experience worsening of their AD, and in the investigator's opinion re-treatment with KY1005 is considered appropriate, they may be considered for enrolment in the LTE (subject to meeting inclusion/exclusion criteria).

The overall study design is presented in Figure 3-1.

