In those patients who achieve  $\geq$  EASI 75 or who attain IGA 0/1 at Week 24, a re-randomisation will occur pre-dose at Day 169 (Week 24) and patients will enter the second study period. The week 24 randomisation will be stratified by IGA response (IGA 0/1 or IGA 2/3/4) at week 24. This will occur irrespective of whichever dose group the patient was randomised to at Baseline including Placebo. Patients will be randomised in a 3:1 manner to be withdrawn from therapy or to continue their pre-Week 24 dose/interval. To maintain the blind, those patients randomised to the withdrawal arm will receive Placebo Q4W. [REDACTED]

At Day 365 (Week 52), patients who have completed the post-Week 24 period and have not experienced loss of clinical response will have an additional 112 days' safety follow-up up to Day 477 (Week 68) and then be discharged from the study. The last dose will be given no later than Day 337 (Week 48) and as such safety follow-up will be 140 days following last dose of IMP. [REDACTED]

The duration of the study will be up to 28 days for screening and then up to approximately Day 477 (Week 68) (to Day 365 [Week 52] plus 112 days safety follow-up, [REDACTED] for all patients unless enrolled into the LTE study (LTS17367) at Day 169 (Week 24) or due to loss of clinical response at or after Day 197 (Week 28). The last dose will be given no later than Day 337 (Week 48).

The IMPs are KY1005 (SAR445229), hereby known as KY1005, or matching Placebo.

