**Analysis of time to event other secondary endpoints**

Time to loss of EASI 75, IGA 0/1, and EASI 50 in patients who re-randomized to Part 2 will be summarized. Kaplan-Meier curves will be presented by the re-randomized treatment groups. When with reasonable number of patients entering each treatment arm during Part 2, two-sided log-rank test (based on stratification factors) and the corresponding p-value might be provided to compare the active treatment group vs corresponding withdrawal placebo arm. Off study treatment data up to Week 52 will be included in the analysis (treatment policy) for patients who discontinued study treatment before Week 52. [Redacted]

[Redacted]  
[Redacted] If applicable, the Kaplan-Meier estimates for the median time, the first and third quartiles might be presented along with approximate 95% CI's.

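### Adding Part 1 dose to the Week 24 stratification would cheaply secure the 3:1 split within each dose, which IGA response alone leaves to chance

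*Protocol*

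**What the plan says.** Protocol 3.6 sets the ratio for Week 24 responders: "Patients will be randomised in a 3:1 ratio to either enter a withdrawal cohort (receiving Placebo Q4W"), with the rest staying on their earlier dose. It names one stratification factor: "This Day 169 (Week 24) randomisation will be stratified by IGA response (IGA 0/1 or IGA 2, 3, 4"). SAP 3.1 repeats the single stratification factor: "The week 24 randomisation will be stratified by IGA response (IGA 0/1 or IGA 2/3/4) at week 24". Protocol 3.1 adds that re-randomisation covers all five arms: "This will occur irrespective of whichever dose group the patient was randomised to at Baseline including Placebo". Nothing visible says that the list is generated within Part 1 arm, and no block size is given.

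SAP 8.3 presents Kaplan-Meier curves by re-randomised group and describes a two-sided log-rank test "to compare the active treatment group vs corresponding withdrawal placebo arm". The test depends on a condition, "When with reasonable number of patients entering each treatment arm during Part 2", and its p-value is optional. No minimum number is defined. The visible text gives no sample size or power for Part 2; parts of Protocol section 10 and SAP section 8 are blacked out.

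**The concern.** Each planned Part 2 contrast lies within a Part 1 dose, but the list protects 3:1 only within two IGA strata pooled over five arms. The factor that defines the comparison is the one left out. Continuing patients are the scarce side, a quarter of responders, so a chance shortfall in one dose weakens the reference against which durability after withdrawal is read at that dose. Protocol 1.5.3 says that this phase will inform later development. Because the SAP makes the test depend on an undefined number of patients, chance could also decide which doses are tested.

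**Working it through.** **1. The plan's own figure.** Protocol 3.6 assumes about 70 patients per arm and 30% dropout to Week 24: 70 × (1 − 0.30) = 49 completers. This reproduces.

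**2. Responders per active dose (assumed).** Protocol Table 1-1 gives Phase 2a EASI 75 rates at Week 16 of 14/27 = 51.9% and 16/27 = 59.3%.
- On 49 completers: 49 × 0.519 = 25.4 to 49 × 0.593 = 29.1.
- On all 70: 70 × 0.519 = 36.3 to 70 × 0.593 = 41.5.
- A lower assumed rate of 40% on 49 gives 19.6.

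I therefore used 20 to 39 per active dose, with 12 to 18 on placebo (25% of 49 and of 70 are 12.3 and 17.5).

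**3. Expected continuing count.** This is n/4: 5.0 at 20 responders, 6.75 at 27 and 9.75 at 39. Stratifying by dose does not change this mean.

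**4. Spread within a dose.** With a list pooled over N responders, the SD is close to √[n × 0.25 × 0.75 × (N − n)/(N − 1)].
- n = 20, N = 92: √(3.75 × 72/91) = 1.72
- n = 27, N = 120: √(5.06 × 93/119) = 1.99
- n = 39, N = 174: √(7.31 × 135/173) = 2.39

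Simulation (8,000 runs, permuted blocks of 4, 65% of responders at IGA 0/1 assumed) gives 1.73, 2.00 and 2.38. With dose as a stratum the SD is 0.56 in each case.

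**5. Precision and risk of a shortfall.** The variance of a within-dose contrast is proportional to 1/c + 1/(n − c), where c is the continuing count. At an exact 3:1 split this equals 16/(3n). The variance loss below is the simulated mean of the ratio of the two. The last two columns give the chance that at least one of the four active doses has 3 or fewer continuing.

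| Responders per dose | SD of c, IGA only | Variance loss, IGA only | 3 or fewer, IGA only | 3 or fewer, IGA and dose |
|---|---|---|---|---|
| 20 | 1.7 | 13% | about 65% | about 0% |
| 27–28 | 2.0 | 9% | 15–17% | about 0% |
| 35 | 2.3 | 6% | 3% | about 0% |
| 39 | 2.4 | 6% | 1% | about 0% |

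With dose as a stratum the variance loss is 1% or less throughout. The average hides the unlucky dose: at n = 27 and c = 4, 1/4 + 1/23 = 0.293 against 16/81 = 0.198, which is about 49% more variance for that dose.

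**6. Power.** Assume a hazard ratio of 1/3, events in half the patients and two-sided alpha 0.05. Schoenfeld's formula gives Φ(√[d × p(1 − p)] × |ln HR| − 1.96), with d events and a fraction p continuing.
- At 35 responders and an exact split: √(17.5 × 0.1875) × 1.099 − 1.96 = 0.03, so power is 51.2%. Averaged over the IGA-only allocation it is 50.0%.
- At 28 responders: 42.9% against 41.6%.
- At 20 responders: 32.4% against 31.2%.

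For 80% power, (1.96 + 0.84)² / (0.1875 × 1.207) gives 35 events per dose pair.

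**The case against.** The strongest reply is that little is lost. Average power moves by about one point, and a weak test stays weak. The small groups come from the 3:1 ratio and the responder count, which stratification does not touch. That stands.

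The risk also depends on the scenario. Table 1-1 is on the full analysis set, so applying its rates to 49 completers may count dropout twice. Entry to Part 2 is by EASI 75 or IGA 0/1, and Protocol 1.5.2 expects improvement beyond Week 16. At 36 to 42 responders per dose the chance that any active dose has 3 or fewer continuing is only 0.5 to 2.6%. For a single named dose the chance is 19% at 20 responders and 0.7% at 35. This stands too, although lower doses may respond less, and 20 per dose is an assumption that no document figure supports directly.

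A reader might infer that some continuing groups become unusable, or that a dose loses its comparator. The documents do not support that. They set no minimum size, they make the test conditional and optional, and they word the time-to-loss endpoints for withdrawn patients, the larger group. Nor is there bias: randomisation stays valid, and 3:1 is protected overall and within IGA strata. The placebo pair receives placebo in both groups, so its split matters little.

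None of this gives a reason to leave out a factor that defines the contrasts and that the IRT must know in order to dispense the continuing dose.

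**Conclusion.** The point holds as a cheap improvement in precision and balance. As written, 3:1 is not protected within the groups that SAP 8.3 compares. The gain is avoiding a chance shortfall in one dose: material if responders are near 20 per dose, modest near 27, and very small near 39. It does not rescue the within-dose comparison, because about 5 to 10 patients per dose would continue either way. The figures rest on assumed blocks of 4, an assumed IGA mix (results barely change between 50% and 70% at IGA 0/1), and Phase 2a Week 16 rates carried to Week 24. If the list is already generated within arm, only the wording is at fault.

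**What to change.** In Protocol 3.6 and SAP 3.1, stratify the Week 24 re-randomisation by Part 1 treatment arm and IGA response (5 × 2 = 10 strata, small blocks). If the list is already made within arm, say so. The IRT already holds the arm, so no one new is unblinded.

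The cost is a list specification and one sentence in each document. The downside is more strata and some incomplete blocks, already reflected in the SD of about 0.6. The change helps only patients not yet re-randomised. The planned start was November 2021 and the SAP versions date from January and May 2023, so many may already have passed Week 24. For those patients, SAP 8.3 can still define the minimum group size for the log-rank test and add a continuing-versus-withdrawn comparison pooled over active doses and stratified by dose.

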3.7 Blinding

The study is double-blind. All patients, the Investigators and their study teams, the Sponsor (with exception of Sponsor Chemistry and Manufacturing Controls [CMC] Clinical Supplies Manager), Clinical Contract Research Organisation (CRO) (with the exception of the unblinded statistician(s), PPD Drug Supply Manager and IRT team), clinical laboratories (except those responsible for drug concentration analysis) and the IDMC will be blinded to treatment regimen until Day 169 (Week 24) has been completed for all patients and the database has been locked for analysis for the Day 169 (Week 24) data. IDMC members can have access to unblinded data sooner than the mentioned timepoint if that is necessary to perform data monitoring activities, and for safety purposes. Thereafter, the study data up to Day 169 (Week 24) will be unblinded to everyone except the study site and patients.

Re-randomisation from Day 169 (Week 24) will not be unblinded to the team (except for those team members listed above).

Study sites and patients will not be unblinded at any stage until after the final Data Base Lock.

If deemed necessary by the IDMC, PPD will select an unblinded statistician among its statisticians.

The work of PPD unblinded staff in support of the IDMC will be performed on an unblinded portal with access to unblinded personnel only.

PPD will generate the trial treatment randomisation codes and provide these to the IRT for inclusion in the IRT system. Randomisation codes will be controlled in the IRT system and procedures for breaking the codes in an emergency will be made available to relevant members of study site staff, the PPD Medical Monitor and the Sponsor Study Responsible medical Officer.

At the assay institutions charged for ADA and PK measurements, samples will be analysed prior to database lock leading to unblinding of responsible bioanalysts. Bioanalysts are excluded from the Operation's Team and results will not be communicated to the sites during the study.

Following written confirmation of database lock, assignment of patients to the analysis populations and finalisation of the study SAP, the study will be unblinded. The date, time, signature and printed name of the persons responsible for database lock, for the assignment of patients to the analysis populations and for treatment code-break (unblinding) will be recorded in order to verify that unblinding occurred in the correct sequence.

For procedures to unblind an individual patient treatment in an emergency, see Section 8.2.1.

Following database lock, the randomisation codes will be made available to all members of Sponsor and CRO staff as required. Randomisation codes will be made available to site staff once all patients have completed the study and the database has been locked.

3.8 Independent Data Monitoring Committee

An IDMC with members independent from the Sponsor and the investigators is implemented to make appropriate recommendations on the conduct of the clinical trial to ensure the protection and the safety of the enrolled patients on the study. The IDMC reviews and analyses, on a regular basis, safety and, if requested, efficacy data throughout the study. Blinded data will primarily form the basis for the IDMCs review. Unblinded data will be available alongside blinded data at the request of the IDMC. Formal data review meetings will be conducted approximately every 2 months to evaluate safety and efficacy data (frequency may need to be reviewed depending on recruitment) and are projected to begin once 10% of participants have received the first dose of IMP or 3 months after first patient dosed, whichever occurs first.

1-Mar-2022

Version number: 1

A detailed IDMC charter will be written to outline the working procedures and duties of the IDMC in detail. The data to be considered by the IDMC, the process for quality control of reports and data, and the documentation of decisions will be described in detail in the mutually agreed charter prior to the study start. The primary responsibility of the IDMC will be to protect the safety of the study patients and will make recommendations to the Sponsor regarding the ongoing conduct of the study. The IDMC may make recommendations to stop the study, continue the study with changes or continue without changes. For example, the IDMC may make a recommendation to terminate a specific dose level, so that if a dose level is not tolerated then no further patients receive a dose that is not safe.

4 STUDY POPULATION

Adult patients with moderate-to-severe AD who have a documented history, within 6 months prior to Baseline, of either inadequate response or inadvisability of topical treatments.

4.1 Number of Patients

Up to 350 patients (approximately 70 patients per treatment arm at Baseline) will be randomised.

4.2 Inclusion Criteria

Patients must fulfil all the following inclusion criteria for entry into the study:

- 1. Adults (18 to <75 years of age) with AD as defined by the American Academy of Dermatology Consensus Criteria [Eichenfield et al., 2014] for 1 year or longer at Baseline (Day 1; prior to first administration of IMP). For United Kingdom, see Section 17.15.2 (Appendix 15).
- 2. EASI of 12 or higher at the Screening Visit and 16 or higher at Baseline.
- 3. IGA of 3 or 4 at Baseline.
- 4. AD involvement of 10% or more of body surface area (BSA) at Baseline.
- 5. Baseline worst/maximum pruritus NRS of ≥4. The baseline weekly average of daily worst/maximum pruritus NRS will be calculated from the 7 consecutive days immediately preceding the Baseline visit. A minimum of 4 daily scores out of the 7 will be required.
- 6. Documented history, within 6 months prior to Baseline, of either inadequate response or inadvisability of topical treatments.

a) Acceptable documentation includes contemporaneous chart notes that record TCS/TCI prescription and treatment outcome, or Investigator documentation based on communication with the patient's treating physician.

1-Mar-2022

[figure not shown]
Version number: 1

- b) Failure to achieve and maintain remission or low disease activity (eg, IGA 0, clear skin to 2, mild disease) despite treatment with TCS of medium to high potency (± topical calcineurin inhibitor as appropriate), applied daily for at least 28 days or for the maximum duration recommended by the product prescribing information (eg, 14 days for super-potent TCS), whichever was shorter. NOTE: Patients who failed systemic therapies intended to treat AD within 6 months preceding screening, such as cyclosporine, methotrexate, azathioprine, and mycophenolate will be also considered as surrogate for having inadequate response to topical therapy. Washout of prior systemic medications must be completed as per the protocol requirements.
- c) Important side effects or safety risks defined as those that outweigh the potential treatment benefits including (but not limited to) hypersensitivity reactions, significant skin atrophy, treatment intolerance and adverse systemic effects, as assessed by the investigator or treating physician.
- 7. Must have applied a stable dose of topical bland emollient (simple moisturiser, no additives [eg, urea]) at least twice daily for a minimum of 7 consecutive days before Baseline.
- 8. Able to complete patient questionnaires, including collection of NRS (pruritus) on each of the 7 days prior to Baseline. For patients who do not have at least 4 daily scores reported during the 7 days immediately preceding the planned randomisation date, randomisation should be postponed until this requirement is met, but without exceeding the 28-day maximum duration for screening.
- 9. Able and willing to comply with requested study visits/telephone visits and procedures.
- 10. Able and willing to provide written informed consent. This document must also actually be presented at the time of inclusion.
- 11. For patients who decide to join the biopsy sub-study at sites selected for skin biopsy collection, be able and willing to provide skin biopsies at required timepoints.

